5.11 Hospitalization and Other Clinical Events

Times to the following clinically relevant events are defined:

- Time to first hospitalization due to a serious adverse event (SAE),
- Time to first hospitalization due to an ALS-related SAE,
- Time to first use of assisted ventilation,
- Time to first placement of a feeding tube,
- Time to King's stage 4a or 4b, and
- Time to first instance of hospitalization for an SAE, feeding tube placement, tracheostomy, initiation of PAV, or death.

Time at risk for each event will be measured from each participant's Baseline Visit. Time to first hospitalization excludes hospitalizations for elective procedures. ALS-related SAEs are those indicated as related to ALS disease progression by the site investigator. Participants who are already using assisted ventilation or have a feeding tube at the time of the Baseline Visit will be excluded from analysis of those endpoints. Death or death equivalent will be considered an outcome for each of the events listed, forming a composite endpoint.

Time at risk for these events will be censored at the Week 24 Visit, if completed, the date of consent withdrawal, if withdrawn, or the last date at which the status of each endpoint is known prior to the end of the Week 24 Visit window for participants lost to follow-up. Time to King's stage 4a or 4b is interval censored between ALSFRS-R assessments.

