Appendix 1. Treatment-emergent Adverse Events of Interest

Events	MedDRA Search Strategy
Infections	SOC “Infections and infestations”
Neisseria infections	HLT “ Neisseria infections”
Potential anaphylactic reactions	Potential anaphylactic reactions are defined via a MedDRA algorithmic approach, which combines a number of different TEAEs/ anaphylactic reaction symptoms that are reported on the same day or on 2 consecutive days, under the condition that use of study drug was still ongoing at the first of these 2 days. Some cases are dependent on the presence of multiple symptoms/ TEAEs and these multiple TEAEs must be on the same onset day or on 2 consecutive days, in order to be classified as an anaphylactic reaction; at least one of the symptoms/TEAEs needs to be serious for the reaction to be classified as a serious anaphylactic reaction. For cases dependent on multiple symptoms the onset date of the reaction will be the onset date of the first preferred term/ symptom experienced, whilst the onset date of serious reactions will be set to the date of the first serious preferred term/symptom. When the reaction consists of multiple TEAEs of different severities, the severity of the reaction is the maximum (i.e., most severe) severity. Similarly, a reaction is classified as related by the investigator if at least one TEAE is related.
Hypersensitivity reactions	SMQ “Hypersensitivity (narrow scope)”
Injection site reactions	TEAEs in MedDRA HLT “Injection site reactions” or HLT “Administration site reactions NEC”.
Drug related hepatic disorders	Narrow SMQ of “Drug related hepatic disorders - comprehensive search (SMQ)” excluding the 2 sub-SMQs of “Liver neoplasms, benign (incl. cysts and polyps) (SMQ)” and “Liver neoplasms, malignant and unspecified (SMQ)”
Malignant or unspecified tumours	SMQ “Malignant or unspecified tumours (SMQ)”
Malignant tumours	SMQ “Malignant tumours (SMQ)”

MedDRA Algorithmic Approach to Anaphylaxis

The standardized MedDRA query (SMQ) “Anaphylactic reaction” consists of three parts:

A narrow search containing PTs that represent core anaphylactic reaction terms:

- **SMQ** Anaphylactic reaction (SMQ)
 - ⊕ **PT** Anaphylactic reaction
 - ⊕ **PT** Anaphylactic shock
 - ⊕ **PT** Anaphylactic transfusion reaction
 - ⊕ **PT** Anaphylactoid reaction
 - ⊕ **PT** Anaphylactoid shock
 - ⊕ **PT** Circulatory collapse
 - ⊕ **PT** Dialysis membrane reaction
 - ⊕ **PT** Kounis syndrome
 - ⊕ **PT** Shock
 - ⊕ **PT** Shock symptom

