 - ⊕ **PT** Type I hypersensitivity

A broad search that contains additional terms that are added to those included in the narrow search.

These additional terms are signs and symptoms possibly indicative of anaphylactic reaction and categorized in B, C or D:

Category B: Upper Airway/Respiratory

⊕ PT Acute respiratory failure⊕ PT Asthma⊕ PT Bronchial oedema⊕ PT Bronchospasm⊕ PT Cardio-respiratory distress⊕ PT Chest discomfort⊕ PT Choking⊕ PT Choking sensation⊕ PT Circumoral oedema⊕ PT Cough⊕ PT Cyanosis⊕ PT Dyspnoea⊕ PT Hyperventilation⊕ PT Irregular breathing⊕ PT Laryngeal dyspnoea⊕ PT Laryngeal oedema⊕ PT Laryngospasm⊕ PT Laryngotracheal oedema	
⊕ PT Mouth swelling⊕ PT Nasal obstruction⊕ PT Oedema mouth⊕ PT Oropharyngeal spasm⊕ PT Oropharyngeal swelling⊕ PT Respiratory arrest⊕ PT Respiratory distress⊕ PT Respiratory dyskinesia⊕ PT Respiratory failure⊕ PT Reversible airways obstruction⊕ PT Sensation of foreign body⊕ PT Sneezing⊕ PT Stridor⊕ PT Swollen tongue⊕ PT Tachypnoea⊕ PT Throat tightness⊕ PT Tongue oedema⊕ PT Tracheal obstruction⊕ PT Tracheal oedema⊕ PT Upper airway obstruction⊕ PT Wheezing
--	---

Category C: Angioedema/Urticaria/Pruritus/Flush

   Allergic oedema	   Pruritus
   Angioedema	   Pruritus allergic
   Erythema	   Pruritus generalised
   Eye oedema	   Rash
   Eye pruritus	   Rash erythematous
   Eye swelling	   Rash generalised
   Eyelid oedema	   Rash pruritic
   Face oedema	   Skin swelling
   Flushing	   Swelling
   Generalised erythema	   Swelling face
   Injection site urticaria	   Urticaria
   Lip oedema	   Urticaria papular
   Lip swelling	
   Nodular rash	
   Ocular hyperaemia	
   Oedema	
   Periorbital oedema	

Category D: Cardiovascular/Hypotension

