   Blood pressure decreased
   Blood pressure diastolic decreased
   Blood pressure systolic decreased
   Cardiac arrest
   Cardio-respiratory arrest
   Cardiovascular insufficiency
   Diastolic hypotension
   Hypotension

An algorithmic approach which combines a number of anaphylactic reaction symptoms in order to increase specificity. A potential anaphylactic reaction is defined as meeting at least one of the following criteria where the different terms occur on either the same day as when an injection was administered or one day after:

A narrow term or a term from Category A;

A term from Category B - (Upper Airway/Respiratory) AND a term from Category C - (Angioedema/Urticaria/Pruritus/Flush);

A term from Category D - (Cardiovascular/Hypotension) AND [a term from Category B - (Upper Airway/Respiratory) OR a term from Category C - (Angioedema/Urticaria/Pruritus/Flush)]

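### The Appendix 1 anaphylaxis algorithm can count an ALS respiratory or choking event as a potential, even serious, anaphylactic reaction, and makes no use of the investigator's ALS attribution

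*SAP*

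**What the plan says.** SAP Appendix 1 lists potential anaphylactic reactions among the TEAEs of interest and builds them from a standardized MedDRA query. There are three routes: a single narrow (core) term; a Category B term with a Category C term; or "A term from Category D - (Cardiovascular/Hypotension) AND [a term from Category B - (Upper Airway/Respiratory) OR a term from Category C".

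- Category B (upper airway/respiratory) includes "PT Respiratory failure", "PT Choking sensation", acute respiratory failure, respiratory arrest, dyspnoea, choking and cough.
- Category D (cardiovascular/hypotension) includes "Cardio-respiratory arrest", cardiac arrest and hypotension.

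Timing is set in two places. The table of events asks for components with onset on the same or adjacent days, "under the condition that use of study drug was still ongoing at the first of these 2 days". The algorithm text asks that "the different terms occur on either the same day as when an injection was administered or one day after". One serious component makes the reaction serious, and one component judged related makes the reaction related.

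Dosing is once daily by subcutaneous injection in both RGA arms (SAP 2.7; Protocol 5.3). SAP 6.6.1 summarizes TEAEs of interest overall, by severity and as serious events. It does not test differences in TEAE proportions, but it estimates differences in TEAE incidence rates with 95% confidence intervals.

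SAP 5.11 defines an attribution for a different purpose, the hospitalization endpoint: "ALS-related SAEs are those indicated as related to ALS disease progression by the site investigator". Appendix 1 does not refer to it.

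**The concern.** Several Category B terms describe what ALS itself does. SAP 5.10 makes respiratory failure secondary to ALS a King's stage (4b), SAP 5.9 treats permanent assisted ventilation as a death equivalent, and the bulbar scale in Protocol Appendix II asks about choking on saliva and after swallowing. Cardiac arrest or hypotension may accompany a terminal or aspiration event. When both kinds of term are recorded close together, the algorithm cannot tell disease progression from allergy.

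At stake is how a safety table reads. A fatal ALS event coded with one term from each list would appear as a serious anaphylactic reaction to an injected peptide. If true reactions are few, even one or two such cases could change the impression the table gives, and nothing in Appendix 1 shows the reader which cases they are.

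**Working it through.** The plan states no figure on this point, so there is none to reproduce. Two checks apply.

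**1. What the rule counts.** The rule from Appendix 1 was applied to illustrative sequences: narrow term, or B and C, or D and (B or C); onsets no more than one day apart; drug ongoing on the first day; injection that day or the day before.

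| Recorded terms | Counted? |
|---|---|
| Respiratory failure alone | No |
| Choking alone | No |
| Cardio-respiratory arrest alone | No |
| Respiratory failure and cardiac arrest, same day, on drug | Yes |
| Respiratory failure day 100, cardiac arrest day 101, last dose day 100 | Yes |
| Choking and hypotension, same day, on drug | Yes |
| Respiratory failure day 100, cardiac arrest day 103 | No |
| Respiratory failure and cardiac arrest, both 5 days after last dose | No |

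The pairing and proximity rules do remove cases. What passes is an ALS event that generates both a B and a D record at nearly the same time on drug.

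**2. What the injection window removes.** A day is in the window if an injection was given that day or the day before. Over the 168-day period with full adherence:

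- daily injection: 168/168 = 100% of days;
- weekly, for comparison only: 24 injections × 2 days = 48, and 48/168 = 29%;
- every 4 weeks, for comparison only: 6 × 2 = 12, and 12/168 = 7%.

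Under daily dosing, a day leaves the window only if no dose was taken that day or the day before. The condition would restrict cases for a drug given at long intervals. Here it restricts almost nothing.

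**3. Size.** The documents give neither a death rate nor the frequency of paired B and D records, so no expected count follows from them. Purely as an illustration, assume a proportion p of 3% to 8% die on drug within 24 weeks, and a fraction q of 10% to 50% of those deaths carry a qualifying pair. Expected false cases are n × p × q:

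- active, n = 120: 120 × 0.03 × 0.10 = 0.36, up to 120 × 0.08 × 0.50 = 4.8;
- placebo, n = 40: 40 × 0.03 × 0.10 = 0.12, up to 40 × 0.08 × 0.50 = 1.6.

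As proportions the arms are identical: 0.36/120 = 0.12/40 = 0.3%, and 4.8/120 = 1.6/40 = 4%. Both p and q are assumptions. The low end is less than one case in the whole regimen.

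**The case against.** The strongest reply is that this is a screen, labelled as potential, taken from a standard query, and working as such screens do. Its main specificity device is the requirement for terms from two categories with close onsets, not the injection window. Each case also carries the investigator's relatedness judgement. Narrow-scope hypersensitivity and injection site reactions are separate events of interest, fatal TEAEs are summarized on their own (SAP 6.6.1), and deaths are listed by participant (SAP 6.5.4). The Master Protocol and Master SAP were not supplied, and they may provide for case review or limit how ALS progression is reported as adverse events.

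Much of this stands. Relatedness in particular is a real aid to interpretation. But it describes a case without separating it from the count, and Appendix 1 does not ask for the count to be shown by ALS attribution.

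A second objection concerns the remedy. If cases attributed to ALS were removed from the headline count, a genuine fatal reaction that an investigator put down to the disease would disappear from it. That would be anti-conservative for a safety endpoint, and it would reduce comparability with counts from the standard query. This objection stands in full, and it is why the full count should remain the main result.

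**Conclusion.** The point holds in a limited form. As written, Appendix 1 can class an ALS respiratory or aspiration event as a potential anaphylactic reaction, and as a serious one if any component is serious. This happens when a Category B and a Category D term are both recorded on the same or adjacent days while on drug. Daily injection makes the injection-day condition nearly empty, and the ALS attribution already defined for SAEs is not used.

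Three stronger conclusions are tempting, and the documents do not support them:

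- *That terminal ALS events in general are counted.* They are not. A single respiratory failure or cardio-respiratory arrest record, a pair several days apart, or a pair after dosing has stopped does not qualify.
- *That 3:1 allocation biases the comparison.* It puts more cases in the larger arm but leaves proportions unchanged, and rate differences allow for arm size. The rule is the same for both RGA arms. A link between this count and efficacy is possible but conditional on a treatment effect, and nothing here measures it.
- *That false cases would overwhelm true ones.* Neither rate is given, and the illustrative range starts below one case.

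Within RGA the consequence is lost specificity in one safety summary. No efficacy inference is affected. The conclusion assumes that documents not supplied do not already require case review or a split by ALS attribution.

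**What to change.** Leave the algorithm and its full count unchanged as the main result. Add to SAP Appendix 1:

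- a supplementary row giving potential anaphylactic reactions, and serious ones, with and without cases in which every component is an SAE that the site investigator attributed to ALS progression as defined in SAP 5.11;
- a listing of all algorithm-positive cases, with component terms, onset days, seriousness, ALS attribution and investigator relatedness, marking each case separated in that row.

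Requiring every component to be so attributed keeps any mixed case in both counts.

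The cost is a few lines of SAP text, one table row and one listing, with no new data collection for SAEs. The downside is reliance on investigator attribution, which the documents define only for SAEs, so pairs with a non-serious component cannot be separated this way. Always showing both counts and listing every separated case limits that weakness.

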Appendix 2. Immunogenicity Analyses

The incidence of anti-drug antibodies (ADA) and anti-PEG antibodies (anti-PEG-ADA) (immunogenicity against zilucoplan) will be measured via dual assay strategy consisting of measuring ADA and anti-PEG-ADA.

The ADA and anti-PEG-ADA status for both active and placebo participants will be determined for each pre-treatment (Baseline) and post-treatment visits (i.e., week 8, week 16 and week 24) where samples are taken for ADA analysis.

- Sample values that are either ‘negative screen’ or ‘positive screen’ and ‘negative immunodepletion’ will be defined as ADA negative
- Sample values that are ‘positive screen’ and ‘positive immunodepletion’ will be defined as ADA positive
- Samples that could not be tested for ADA status due to inadequate sample volume, mishandling, or errors in sample collection, processing, storage, etc, will be defined as Missing.

The following ADA classifications will be derived from the sample ADA status.

Table: ADA Classification

Classification	Classification Label	Definition
1	Pre-ADA negative – treatment induced ADA negative	Participants who are ADA negative at Baseline and ADA negative at all sampling points post-Baseline
2	Pre-ADA negative – treatment induced ADA positive	Participants who are ADA negative at Baseline and ADA positive at any sampling point post-Baseline. It also includes participants who have a missing pre-treatment sample (either missing or insufficient volume) at Baseline with one or more ADA positive post-Baseline samples.
3	Pre-ADA positive – treatment reduced ADA	Participants who are ADA positive at Baseline, and ADA negative at all sampling points post-Baseline
4	Pre-ADA positive – treatment unaffected ADA	Includes participants who are ADA positive at Baseline and ADA positive at any sampling point post-Baseline (including Observation Period) with titer values of the same magnitude as Baseline (less than a predefined fold difference from the Baseline value which will be defined within the validation of the assay, i.e., MSR of the assay).

Table: ADA Classification

Classification	Classification Label	Definition
5	Pre-ADA positive – treatment boosted ADA positive	Includes participants who are ADA positive at Baseline and ADA positive at any sampling point post-Baseline (including Observation Period) with increased titer values compared to Baseline (greater than a predefined fold difference increase from Baseline value which will be defined within the validation of the assay, i.e., MSR of the assay).
6	Inconclusive	Participants who have an ADA positive Baseline sample and some post-Baseline samples are missing, while other post-Baseline samples are ADA negative.
7	Treatment emergent ADA positive	Combination of 2 and 5
8	Pre-ADA positive	Combination of 3, 4, and 5

MSR=minimum significant ratio.

In addition to the ADA classifications above, for the purpose of exploring the impact of ADA on PK, and safety endpoints, the following definitions will be used:

- Cumulative ADA status (positive/negative). If a study participant has had at least one positive sample at any time point (including unscheduled visits) up to and including the given time point, that study participant will be counted as positive at that time point, regardless of any subsequent negative measurements.
- Overall ADA status. A study participant will be classified as overall ADA Positive if at least one post-Baseline measurement (including unscheduled visits) is Positive. A study participant will be classified as overall ADA Negative if at all post-Baseline visits the ADA status is Negative.

The same definitions and classifications will be used for anti-PEG-ADA.

The following outputs will be presented for the SRO sample.

- Number and percentage of study participants with positive, negative or missing sample ADA status at each visit will be summarized by treatment group.
- Number and percentage of study participants in each of the ADA classifications presented will be summarized by treatment group.
- The prevalence of immunogenicity (Classification 2, 3, 4 and 5), defined as the (cumulative) proportion of study participants having ADA positive samples (including pre-ADA positive) at any point up to and including that time point will be summarized by treatment group. Missing samples will not be included in the denominator.

- The first occurrence of treatment-emergent ADA positive (Classification 2 and 5) will be summarized using frequency and percentage at each post-Baseline visit by treatment group. Study participants will be counted only once in the numerator based on the earliest visit at which treatment-emergent ADA positivity is observed. At other visits, study participants will be counted in the denominator (assuming a measurement is available). Missing measurements will not be included in the denominator.
- The time to achieving treatment-emergent ADA positivity, separated by treatment group, will be summarized and analyzed based on Kaplan-Meier methods. Study participants will be considered to have an event at the time point at which treatment-emergent ADA positive is first achieved. Participants who never had a treatment-emergent ADA positivity will be censored at the date of their last visit. This will also be plotted graphically.

The same tables will be provided for anti-PEG-ADA by treatment group.

Relationship between ADA and Safety Endpoints

TEAEs will be summarized by ADA status using the following categories:

- AEs starting before first treatment emergent ADA positive result
- AEs starting on or after first treatment emergent ADA positive result
- AEs for study participants who were overall ADA negative

Each TEAE will be classified according to whether it occurred before the first treatment emergent positive result, on or after the first treatment positive result, or for a study participant that remained treatment negative post-baseline. If a participant has multiple reports of the same AE (i.e., those which code to the same preferred term) emerging both prior to first ADA positive result and after first ADA positive result, both events will be counted in the appropriate category.

The following AE outputs will be presented this way:

- Overall summary of TEAEs (i.e., the number of events and proportion of participants experiencing any TEAE, any serious TEAE, any severe TEAE, any related TEAE, any TEAE leading to discontinuation of study drug, and any fatal TEAEs) by treatment group and by ADA status
- Incidence of TEAEs of interest by treatment group and by ADA status
Presented for any hypersensitivity reactions and any injection site reactions (as defined in Appendix 1) and any autoimmune disorders (defined by the MedDRA HLGT of Autoimmune disorders).

The AE analyses above will be repeated by anti-PEG-ADA status.

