6 REGIMEN SCHEDULE

6.1 Placebo-Controlled Period

In addition to procedures in the Master protocol, the following regimen specific procedures will be conducted during the study:

- Home Spirometry
 - Note: Home spirometry should be collected within the visit window but will occur while the participant is not in the clinic (at home or other remote location).
- ALSAQ-40
- CNS Bulbar Function Scale
- Smartphone installation and removal
- Voice recording
- Dispense investigational product to participant
- Neisseria Meningitidis Vaccination
 - **Note: Booster vaccinations should be administered in accordance with SOC. Please refer to SOC and vaccination worksheet for details about timing.**
- Anti-drug Antibody Sampling
- Zilucoplan Plasma PK Analysis
- Zilucoplan Pharmacodynamic Analysis
- Zilucoplan Peripheral Blood Biomarker Samples

Participants may be required to reconsent to the regimen if new procedures or information is added in the future. Should a participant need to reconsent, this should occur during the participant's next in-person visit. If the participant's next in-clinic visit is conducted remotely, reconsent may also be completed remotely using the following procedures:

1. The site staff sends a copy of the informed consent form to the participant.
2. The participant reads through the consent form but does not sign.
3. The Site Investigator, or other study staff member approved and delegated to obtain informed consent, contacts the participant and reviews the informed consent form with the participant.
4. The participant signs the informed consent form and returns the original signed consent form back to the site.
5. Once received at the site, the individual who consented the participant signs the informed consent form.

Modifications to Regimen Schedule

Designated visits in the Schedule of Activities (i.e., Week 4, Week 8, and Week 16) may be conducted via telemedicine (or phone if telemedicine is not available) with remote services instead of in-person if needed to protect the safety of the participant due to a pandemic or other reason. If a planned in-clinic visit is conducted via telemedicine (or phone if telemedicine is not available) with remote services, only selected procedures will be performed. Instructions on how to document missed procedures are included in the MOP.

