In addition to the procedures in the Master Protocol that should be conducted during the phone or telemedicine and remote visits, the following regimen-specific procedures should be completed:

- Home Spirometry (Week 8 and 16 only)
- Voice Recording
- CNS Bulbar Function Scale (Week 8 and 16 only)
- *Neisseria Meningitidis* Vaccination booster shots

Details on collection of the CNS Bulbar Function Scale, dispensing IP during remote visits, and documenting participants' willingness to participate in OLE are described in the MOP.

Blood samples for anti-drug antibody sampling, PK and PD analyses, and peripheral blood biomarker samples are not collected during the remote visits by the home health agency and this should be recorded as such in the applicable source documentation and EDC.

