6.1.11 Process for Early Terminations

Participants who early terminate from the study and do not complete the protocol will be asked to be seen for an in-person Early Termination Visit and complete a Follow-Up Safety Call. If a participant is not able to be seen in-person, safety assessments and others that can be conducted remotely should be performed.

The in-person Early Termination Visit should be scheduled as soon as possible after a participant early terminates. If the participant early terminates during the placebo-controlled portion of the Regimen, all assessments that are collected at the Week 24 in-clinic visit should be conducted. If the participant early terminates during the OLE phase, all assessments that are collected at the OLE Week 52 in-clinic visit should be conducted. The Follow-Up Safety Call should be completed approximately 40 days after the last dose of study drug.

If the Early Termination Visit occurs approximately 40 ± 3 days after the last dose of study drug, the information from the Follow-Up Safety Call can be collected during the Early Termination Visit, and a separate Follow-Up Safety Call does not need to be completed. If the in-person Early Termination Visit does not occur within 40 ± 3 days of the last dose of study drug, the Follow-Up Safety Call should occur approximately 40 ± 3 days after the last dose of study drug and the Early Termination Visit will be completed after the Follow-Up Safety Call.

Note: Participants should be instructed to continue using effective contraception for at least 40 days after their last dose of study drug.

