Abbreviations: ALD = after last dose, ALS = amyotrophic lateral sclerosis, ALSAQ-40 = ALS Assessment Questionnaire, ALSFRS-R = ALS Functional Rating Scale Revised, BP = blood pressure, C = completed only if the visit is conducted in-clinic, CBC = complete blood count, Cln = Clinic visit, CNS-BFS = Center for Neurologic Study Bulbar Function Scale, CSF = cerebrospinal fluid, C-SSRS = Columbia-Suicide Severity Rating Scale, d = day, DNA = deoxyribonucleic acid, ECG = electrocardiogram, LFTs = liver function tests, MP = Master Protocol, PD = pharmacodynamic, Phn = Phone visit, PK = pharmacokinetic, RGA = the zilucolan regimen, Scrn = Screening Visit.

¹ Master Protocol (MP) screening procedures must be completed between 42 days and 1 day prior to the Baseline Visit. If initial administration of conjugate and serotype B meningococcal vaccines is required, then MP screening procedures must be completed no fewer than 14 days prior to the Baseline Visit.

² RGA regimen-specific screening procedures must be completed no more than 41 days prior to the Baseline Visit. If initial administration of conjugate and serotype B meningococcal vaccines is required, then RGA regimen-specific screening procedures must be completed no fewer than 14 days prior to the Baseline Visit. Otherwise, RGA regimen-specific screening procedures may be completed on the same day as the Baseline Visit.

³ Participants should be instructed to hold the morning dose of study drug on the day of the Week 8, 16, and 24 study visits. Study drug should not be taken until after study visit procedures are complete.

⁴ Participants who are participating into the Open-label Extension (OLE) at the time scheduled for the Follow-up Safety Call will not complete a Follow-up Safety Call. Participants who continue into the OLE and then terminate prior to the time scheduled for the Follow-up Safety Call should be asked to complete a Follow-Up Safety Call.

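### The Kaplan-Meier curve for time to treatment-emergent ADA is censored at the last visit of any kind rather than the last ADA sample, so untested participants can remain at risk as event-free; the effect is small and confined to this output

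*SAP*

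**What the plan says.** SAP Appendix 2 plans a Kaplan-Meier summary of time to treatment-emergent ADA positivity by treatment group, and the same for anti-PEG-ADA. On events: "Study participants will be considered to have an event at the time point at which treatment-emergent ADA positive is first achieved". On censoring: "Participants who never had a treatment-emergent ADA positivity will be censored at the date of their last visit".

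The same appendix gives the sampling times after Baseline: "post-treatment visits (i.e., week 8, week 16 and week 24) where samples are taken for ADA analysis". Two of these three visits need not be in person. Protocol 6.1 says: "Designated visits in the Schedule of Activities (i.e., Week 4, Week 8, and Week 16) may be conducted via telemedicine". It adds: "Blood samples for anti-drug antibody sampling, PK and PD analyses, and peripheral blood biomarker samples are not collected during the remote visits". The schedule in SAP 2.9 agrees. It codes the Week 8 and Week 16 ADA samples C, where "C = completed only if the visit is conducted in-clinic".

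Other contacts carry no ADA sample. Weeks 2, 12 and 20 are phone visits without regimen-specific procedures (Protocol 6.1, Telephone Visit sections), and the safety call about 40 days after the last dose is also by phone (Protocol 6.1, Follow-Up Safety Call section). An in-person Early Termination Visit repeats the Week 24 assessments, including ADA. If that is not possible, Protocol 6.1.11 says: "If a participant is not able to be seen in-person, safety assessments and others that can be conducted remotely should be performed".

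**The concern.** ADA status is known only where a sample was taken. A rule that censors at the last visit, without tying that visit to a sample, credits event-free time during which nobody looked. Take a participant with a Baseline sample, a remote Week 8 visit, a Week 12 phone call, then drop-out without an in-person final visit. This participant was never tested after Baseline, yet counts as at risk and negative at the Week 8 event time.

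The SAP is stricter for other endpoints that are seen only at assessments. HHD0 and HHD0² are censored at the last HHD assessment (SAP 5.4) and treated as interval censored (6.5.6). Time to King's stage 4a or 4b is interval censored between ALSFRS-R assessments (5.11, 6.5.4).

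Immunogenicity is the one regimen-specific safety endpoint (SAP 4.3), so a curve that leans low by construction deserves correction. The term 'last visit' is also undefined: two programmers could disagree on whether the safety call counts.

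**Working it through.** The documents state no ADA incidence or precision for this analysis, so there is no planned figure to reproduce. The check compares two censoring rules on the same events.

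**Direction.** The 24-week Kaplan-Meier incidence is F = 1 − Π(1 − d_j/n_j), with d_j events and n_j at risk at event time j. The d_j are identical under both rules. Every participant is censored no earlier under the last-visit rule, so each n_j is at least as large, and F is equal or lower. It is strictly lower only if someone passes an event time unsampled, has no later sample, and has a later contact that counts as a visit.

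**Hand example.** Nominal visit days; 120 participants, the planned active arm (Protocol summary). Assumed: 100 are fully sampled, with 5 first positives at each of days 56, 112 and 168; the other 20 are never positive.

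| The other 20 | Last-visit rule | Last-sample rule |
|---|---|---|
| (a) No post-baseline sample; last contact Week 20 phone | 1 − (115/120)(110/115)(85/90) = 13.4% | 1 − (95/100)(90/95)(85/90) = 15.0% |
| (b) Last sample Week 8, Week 16 remote, last contact Week 20 phone | 1 − (115/120)(110/115)(85/90) = 13.4% | 1 − (115/120)(90/95)(85/90) = 14.3% |
| (c) Last sample Week 8, last contact Week 12 phone | 1 − (115/120)(90/95)(85/90) = 14.3% | 14.3% |

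In (c) no event time lies between the last sample and the last contact, so nothing changes. A participant with remote Weeks 8 and 16 who is sampled at Week 24 likewise contributes the same to both curves at nominal days.

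**Simulation over assumed ranges** (30 runs of 4,000 per scenario). Inputs, none of them in the documents:
- ADA onset of 3% or 10% per 8-week interval, so the true 24-week incidence is 1 − 0.97³ = 8.7% or 1 − 0.90³ = 27.1%;
- 0, 20 or 50% of Week 8 and 16 visits remote;
- 10 or 25% drop-out;
- 0, 50 or 100% of early terminators sampled;
- safety call counted as a visit or not.

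The last-visit estimate was 0 to 0.9 points below the last-sample estimate at 8.7% true incidence, and 0 to 2.5 points below at 27.1%. That is 0 to about 10% relative, and never higher. Results at 27.1%, with 25% drop-out and 50% remote:

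| Early terminators sampled | Safety call counted | Last-visit | Last-sample | Difference (points) |
|---|---|---|---|---|
| all | no | 29.35% | 29.35% | 0.00 |
| all | yes | 27.63% | 29.35% | −1.73 |
| half | yes | 26.54% | 28.69% | −2.15 |
| none | no | 27.27% | 27.89% | −0.62 |
| none | yes | 25.39% | 27.89% | −2.50 |

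(Differences were taken before rounding.) Whether the safety call counts drives most of the gap. The last-visit curve lies on either side of the true 27.1% (25.39% to 29.35%), because positives are detected late and at irregular times. Last-sample censoring does not cure that.

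**Which estimator recovers the truth.** In a further simulation with an assumed true incidence of 18%:

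| Estimator | Range |
|---|---|
| Last-visit Kaplan-Meier, safety call counted | 16.4–18.0% |
| Last-visit Kaplan-Meier, safety call not counted | 17.5–19.0% |
| Last-sample Kaplan-Meier | 17.9–19.3% |
| Interval-censored estimator | 17.8–18.2% |

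**The case against.** The strongest case against acting has four parts.

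- **Narrow reach.** SAP 6.6.6 delivers immunogenicity as proportions positive, negative and missing, by visit and at any post-baseline visit. In Appendix 2 the prevalence and first-occurrence tables drop untested samples: "Missing measurements will not be included in the denominator". The Kaplan-Meier curve is one descriptive output, reported separately by the manufacturer. This stands. Per-visit percentages and a cumulative curve are also different quantities, so a difference between them is not in itself a contradiction.
- **Last-sample Kaplan-Meier is no closer to the truth.** At an assumed 18% it gave 17.9–19.3%. This stands, and it is why moving the censoring date alone is not enough.
- **The mechanism needs a conjunction.** Week 24 is not among the visits that may be remote, and early terminators are asked to attend in person. This stands. Remote participation alone does not bias the curve.
- **'Last visit' may mean a sampling visit.** Appendix 2 names Weeks 8, 16 and 24 as its post-treatment visits. On that reading most of the effect disappears. The text does not say so, however, and a remote Week 8 or Week 16 visit would still count without a sample.

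A reader might infer that the trial's ADA incidence as a whole will be understated, particularly among remote participants. The documents do not support that: the tables that report incidence and prevalence do not use this rule, and remote participants sampled later contribute the same under either censoring rule.

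**Conclusion.** The censoring rule is loose and should be corrected, but the consequence is limited. The Kaplan-Meier curves for ADA and anti-PEG-ADA are never higher than with last-sample censoring and can be lower, by 0 to about 10% relative (at most 2.5 points in the scenarios examined). The direction is certain; the size rests entirely on assumed ADA, remote-visit, drop-out and final-sampling rates, and largely on whether the safety call is a visit. A claim that the curve falls below the true incidence would go too far, since under the same assumptions it also landed above it. Efficacy inference and the other immunogenicity tables are untouched. The case for change is that the SAP already treats similar endpoints as interval censored, and that an interval-censored estimator recovered the assumed truth where neither Kaplan-Meier version did so reliably.

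**What to change.** Replace the censoring sentence in SAP Appendix 2 with:

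> Time to treatment-emergent ADA positivity is interval censored between the last negative (or Baseline) and first positive sample and estimated with an interval-censored non-parametric (Turnbull) estimator. Participants without treatment-emergent positivity are right-censored at their last evaluable ADA sample. Those with no evaluable post-baseline sample are excluded and counted.

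Apply the same to anti-PEG-ADA. For participants positive at Baseline, the lower limit should be the last sample that does not meet the treatment-boosted definition. Tying censoring to the sample also removes the question of whether the safety call is a visit.

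Cost: a wording change, a different derived variable and a different estimator to program. No new data are needed. The denominator becomes slightly smaller and the intervals wider.
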